3.5 Projected statistical analyses

In response to the first research question, descriptive analyses will be conducted based on measurement of the clinical and organizational quality indicators identified in the acute phase. Medians and interquartile ranges, means and standard deviations and proportions will be used to describe performance of care and services for each center under study and comprehensively for all three centers. Additionally, a contextual description of each center will be presented using data collected on the hospitals' characteristics.

Results of the first objective will highlight indicators that do or do not meet the guidelines for quality of care for persons with ischemic stroke and their caregivers. For indicators presenting extensive data, regression analyses will be performed to identify the determinants likely to influence results regarding these indicators.

Dependent variables are clinical or organizational quality indicators, while independent variables correspond to the sociodemographic characteristics and clinical profile of patients with ischemic stroke. Type of regression analysis will vary consistent with the nature of the dependent variables (dichotomous or continuous) and their distribution (parametric or nonparametric tests).

A univariate regression analysis will first allow us to associate determinants (independent variables) with results for the indicators (dependent variables). Variables with a statistically significant association will then be introduced into a linear or logistic regression model. Additionally, these regression analyses will include

confounding variables that may also influence results from the measurement of clinical and organizational quality indicators. To be statistically significant, results must obtain a value of $p < 0.05$ and have a confidence interval of 95 %. All statistical analyses will be conducted using SPSS 28.0 software. Results will be presented comprehensively for the three centers; they may also be presented individually for the secondary and tertiary centers to see if the associations in them are similar or different. If the number of records in one of these hospitals is not enough for statistical power, the analysis will not be performed.

4. Consent process

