Numerator: Number of post-stroke patients with one or more of these post-stroke complications during hospitalization

Denominator: Total number of post-stroke patients

Indicator 18

Proportion of patients given a carotid Doppler test within 24 hours

Numerator: Number of post-stroke patients given a carotid Doppler test within 24 hours

Denominator: Total number of post-stroke patients

Effectiveness

Indicator 19

Proportion of patients who die from stroke in hospital within 7 days and within 30 days following admission

Numerator 1: Number of patients who die from stroke within 7 days following admission to hospital

Numerator 2: Number of patients who die from stroke within 30 days following admission to hospital

Denominator: Total number of ischemic stroke patients hospitalized or discharged from hospital

Indicator 20

Proportion of patients with severe disability at discharge (mRS 0-3) (Calculate proportion of patients for each modified Rankin score, mRS of 1 to 5.)

Numerator: Number of patients with a modified Rankin score (mRS) between 0 and 3 at discharge

Denominator: Total number of patients with a modified Rankin score recorded at discharge

Indicator 21

Proportion of patients with increased shoulder pain based on pain intensity score evaluated with a valid tool using reference data during hospitalization

Numerator: Number of post-stroke patients with increased shoulder pain based on pain intensity score evaluated with a valid tool

Denominator: Number of post-stroke patients with shoulder pain

Indicator 22

Proportion of patients readmitted to short-term hospital care for a stroke-related issue after discharge (post 30 days)

Numerator: Number of patients readmitted to short-term hospital care for a stroke-related issue within 30 days after discharge

Denominator: Total number of post-stroke patients re-hospitalized after discharge

Continuity

Indicator 23

Proportion of post-stroke patients prescribed an anticoagulant, lipid-lowering medication, an antiplatelet, an antihypertensive, or a hypoglycemic at discharge (Result per medication)

Numerator: Number of post-stroke patients prescribed an anticoagulant, lipid-lowering medication, an antiplatelet, an antihypertensive, or a hypoglycemic at discharge

Denominator: Total number of post-stroke patients prescribed one or more medications

Indicator 24

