Proportion of post-stroke patients with a record that includes a therapeutic nursing plan (TNP), an individualized intervention plan (IIP) or a care plan (CP)

Numerator: Number of post-stroke patients with a record that includes a therapeutic nursing plan (TNP), an individualized intervention plan (IIP) or a care plan (CP)

Denominator: Total number of post-stroke patients

Indicator 25

Transfer at discharge: Proportion of post-stroke patients transferred at discharge to inpatient rehabilitation, outpatient rehabilitation, return to residence, long-term care centre or palliative care (Result by patient's place of transfer)

Numerator: Number of post-stroke patients transferred to inpatient rehabilitation, outpatient rehabilitation, return to residence, long-term care center or palliative care

Denominator: Total number of post-stroke patients discharged from hospital

Indicator 26

Proportion of post-stroke patients referred at discharge to a secondary prevention program (Specify type of referral)

Numerator: Number of post-stroke patients referred at discharge to a secondary prevention program

Denominator: Total number of post-stroke patients discharged

Reactivity

Indicator 27

Proportion of post-stroke patients and caregivers met by the team to discuss management of the patient and his or her needs following discharge

Numerator: Number of post-stroke patients and caregivers met by the team to discuss management of the patient and his or her needs following discharge

Denominator: Total number of post-stroke patients discharged

Indicator 28

Proportion of post-stroke patients and caregivers instructed prior to discharge on the following stroke-related topics of interest: modifiable risk factors, warning signs and symptoms of stroke, how to activate medical emergency services, post-discharge services available, prescribed medications and community resources

Numerator: Number of post-stroke patients and caregivers instructed prior to discharge on these topics of interest

Denominator: Total number of post-stroke patients

Indicator 29

Proportion of post-stroke patients and caregivers who were invited to participate in advance planning of care or had a documented conversation with a health professional regarding resuscitation and level of care

Numerator: Number of post-stroke patients who were invited to participate in advance planning of care or had a documented conversation with a health professional regarding resuscitation and level of care

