H2. Date and time of death DD/MM/YYYY ____ / ____ / ____ HH: MIN ____ : ____
H3. Short stay discharge  1-No  2-Yes  3-Not applicable  99-Missing data
H4. Date and time of short stay discharge DD/MM/YYYY ____ / ____ / ____ HH: MIN ____ : ____
H5. Date and time of stroke unit discharge

DD/MM/YYYY ____ / ____ / ____ HH: MIN ____ : ____	
H6. Date and time of intensive care unit discharge DD/MM/YYYY ____ / ____ / ____ HH: MIN ____ : ____	
H7. Presence in the record of functional independence evaluation using modified Rankin Scale (mRS)  1-No  2-Yes  3-Not applicable  99-Missing data	
H8. Clinician performing the functional independence evaluation using modified Rankin Scale (mRS) in the record  1-Nurse  2-Neurologist  3-Occupational therapist  4-Other: _____  99-Missing data	
H9. mRS result at discharge: _____	
H10. Anticoagulant prescribed at discharge  1-No  2-Yes  3-Not applicable  99-Missing data	
H11. Lipid-lowering medication prescribed at discharge  1-No  2-Yes  3-Not applicable  99-Missing data	
H12. Antiplatelet prescribed at discharge  1-No  2-Yes  3-Not applicable  99-Missing data	
H13. Hypertensive prescribed at discharge  1-No  2-Yes  3-Not applicable  99-Missing data	
H14. Hypoglycemic prescribed at discharge  1-No  2-Yes  3-Not applicable  99-Missing data	
H15. Discussion with patient about targeted goals for discharge  1-No  2-Yes  3-Not applicable  99-Missing data	
H16. Individualized intervention plan developed with patient and caregivers  1-No  2-Yes  3- Not applicable  99-Missing data	

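### Indicator 23 counts only patients with a prescription in its denominator, so untreated survivors drop out and each class result becomes a share among treated patients

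*Protocol*

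**What the plan says.** Appendix 1 heads Indicator 23: "Proportion of post-stroke patients prescribed an anticoagulant, lipid-lowering medication, an antiplatelet, an antihypertensive, or a hypoglycemic at discharge (Result per medication"). The population named is post-stroke patients, and one result is to be given for each drug class.

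The numerator is pooled over the classes: "Numerator: Number of post-stroke patients prescribed an anticoagulant, lipid-lowering medication, an antiplatelet, an antihypertensive, or a hypoglycemic at discharge".

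The denominator is "Denominator: Total number of post-stroke patients prescribed one or more medications". It names no drug class and no time point.

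The indicators that follow in the discharge group use a wider base. Indicator 25 has "Denominator: Total number of post-stroke patients discharged from hospital". Indicators 26 and 27 have "Denominator: Total number of post-stroke patients discharged".

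The collection sheet (Appendix 2, section H) records discharge drugs in five items, from "H10. Anticoagulant prescribed at discharge" to "H14. Hypoglycemic prescribed at discharge". These are the same five classes. Each is coded no, yes, not applicable (3) or missing (99). No item records any other drug at discharge. Pre-stroke drugs are recorded separately, in C6.

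Section 3.5 states what the indicators are for: "Results of the first objective will highlight indicators that do or do not meet the guidelines for quality of care".

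**The concern.** A prescribing indicator has to be able to register a patient who was not prescribed. This denominator conditions on the outcome being measured: a patient enters only by having received a prescription. The survivor sent home with nothing is deleted instead of counted in the denominator alone.

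Hypothesis 1 of the protocol concerns gaps between guidelines and practice, and section 3.5 uses the indicators to show where they lie. A denominator that removes untreated survivors hides part of that gap. It may hide different amounts at the three centres, which hypothesis 2 sets out to compare. Section 3.5 also makes the indicators dependent variables in regressions. If this denominator were carried into those models, patients would be selected on the outcome.

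**Working it through.** The plan gives no expected value, target or rate for Indicator 23, so there is no figure to reproduce. The check is on the ratios that the definition implies.

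**Inputs**
- N = 130 planned records (section 3.3.2), standing in for patients discharged alive. This is for illustration only, because some patients will die in hospital.
- u = patients discharged with no prescription. Not in the documents; assumed 0 to 26, which is 0% to 20%.
- k = patients prescribed a given class. Assumed 80.
- o = patients discharged only on drugs outside the five classes. Not in the documents.

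**Class results**
- As written: k/(N − u).
- Over all discharged alive: k/N.
- Ratio of the two: N/(N − u) = 1/(share with any prescription). This gives 1/0.95 = 1.05, 1/0.90 = 1.11 and 1/0.80 = 1.25.

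| u | As written | Over all 130 | Difference (points) | Factor |
|---|---|---|---|---|
| 0 | 80/130 = 61.5% | 61.5% | 0 | 1.00 |
| 5 | 80/125 = 64.0% | 61.5% | 2.5 | 1.04 |
| 13 | 80/117 = 68.4% | 61.5% | 6.8 | 1.11 |
| 26 | 80/104 = 76.9% | 61.5% | 15.4 | 1.25 |

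**Unequal distortion between centres.** Take centres of 75 and 45 records (the planned tertiary and secondary numbers), each prescribing a class to 60% of all its patients (45/75 and 27/45). With 4 untreated at the first and 9 at the second (assumed), the written definition gives 45/71 = 63.4% and 27/36 = 75.0%. Equal prescribing appears as a gap of 11.6 points.

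**Combined proportion, medications read as the five classes.** Numerator and denominator are then the same patients: (N − u)/(N − u) = 100% for every u. Over all 130 it would be 125/130 = 96.2%, 117/130 = 90.0% and 104/130 = 80.0% for u = 5, 13 and 26.

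**Combined proportion, medications read as any drug.** The result is (N − u − o)/(N − u). With u = 13 and o = 3, 6 and 13 it is 114/117 = 97.4%, 111/117 = 94.9% and 104/117 = 88.9%. Over all 130 the figures are 87.7%, 85.4% and 80.0%. Untreated patients are still lost, and the sheet cannot identify this denominator because no item records other discharge drugs.

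**The case against.** **The output is per class.** A reader might infer that the indicator will sit at or near 100%. The heading asks for a result per medication, so five class proportions are planned and none is forced to 100%. The 100% result applies only to a combined figure built from H10 to H14. Near 100% under the any-drug reading would be an assumption about o. This objection stands and limits the point to the class results and to any pooled figure.

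**Leaving patients untreated need not help a centre.** The centre example above holds the all-patient rate fixed. From 80/117 = 68.4%, if one patient who would have received the class receives nothing, the result becomes 79/116 = 68.1%, which is lower. If the patient would have received only other classes, it becomes 80/116 = 69.0%. The general claim that omission is rewarded does not hold.

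**A corrected rate need not be lower.** Suppose 100 patients are discharged alive and 90 have a prescription. A class that applies to 25 and is given to all 25 reads 25/90 = 27.8% as written, 25/100 = 25% over all discharged, and 25/25 = 100% over those to whom it applies. Differences in how many patients a class applies to therefore remain under an all-discharged denominator. That is a separate matter from the defect here.

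**Code 3 is undefined.** Not applicable appears on many items in Appendix 2, including short-stay discharge, discharge goals and discharge education. It may mean death or transfer, not that the class did not apply. Dropping code 3 does not by itself give an eligibility-based rate.

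**Other indicators use subsets.** Indicators 10, 16 and 21 do so, but they condition on screening, reperfusion therapy or shoulder pain, which are distinct from the outcome. Indicator 23 conditions on the outcome. Leaving out in-hospital deaths is proper, and a discharged-alive denominator does that without removing untreated survivors.

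**Conclusion.** The denominator is wrong as written. It conflicts with the indicator's own heading and with Indicators 25 to 27, and it removes patients whom the indicator should count as not prescribed. Class results are inflated, relative to all patients discharged alive, by 1/(share with any prescription). At assumed shares of 95%, 90% and 80% that is 1.05, 1.11 and 1.25. The true share is not in the documents and the effect could be small. The factor can differ between centres, so comparisons are affected as well as levels. A combined proportion built from H10 to H14 carries no information.

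This assumes that the denominator refers to prescriptions at discharge, which its wording leaves open.

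It should be fixed but is not critical: it is one of 29 indicators in a descriptive study, and the patient-level data needed to correct it are already collected.

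**What to change.** - In Appendix 1, change the Indicator 23 denominator to post-stroke patients discharged alive, with H1 identifying deaths. This agrees with the heading and with Indicators 25 to 27.
- Report each of the five classes separately over that denominator. Drop the combined proportion, or give it only over all patients discharged alive.
- Report the number coded 3 in H10 to H14, per class and centre.
- Have the investigators define code 3 for these items. Only if it means that the class did not apply to the patient, also report each class over patients not coded 3. That rate may be higher or lower than the one now planned. With 100 discharged alive, 90 with a prescription and 70 given the class, the written result is 70/90 = 77.8%. Excluding 20 coded 3 gives 70/80 = 87.5%; excluding 5 gives 70/95 = 73.7%.

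The denominator change costs one line and needs no new data. The additional rate costs a clinical definition of code 3, best settled before records are abstracted.
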